## **17 ENDOCRINE DISORDERS**

Treatment-emergent increases in thyroid-stimulating hormone (TSH) have been observed with cabozantinib treatment. Currently available data are insufficient to determine the mechanism of thyroid function test alterations and its clinical relevance. Routine monitoring of thyroid function and assessments for signs and symptoms associated with thyroid dysfunction is recommended before initiation and during treatment with cabozantinib. Management of thyroid dysfunction (e.g. symptomatic hypothyroidism) should follow accepted clinical practice guidelines.

## **18 MUSCULOSKELETAL AND CONNECTIVE TISSUE DISORDERS**

Cabozantinib appears to represent minimal risk of adverse musculoskeletal effects based on nonclinical GLP-compliant toxicology studies. The development of new or progressive, unexplained musculoskeletal symptoms such as pain or weakness should be assessed for underlying causes.

Rhabdomyolysis has been reported. Cabozantinib should be discontinued in subjects with serious and life-threatening rhabdomyolysis and interrupted if less severe forms occur when

there are no other clear causes. Re-initiation of cabozantinib treatment must be discussed with and approved by the sponsor. Therapy of rhabdomyolysis should include supportive care and standard medical intervention.

## **19 RESPIRATORY, THORACIC AND MEDIASTINAL DISORDERS**

Dyspnoea has been reported in clinical studies with cabozantinib. Symptoms should be managed according to locally accepted clinical practice including an assessment for underlying causes. Pulmonary embolism should be considered as possible causes for new onset dyspnoea given the risk of thrombosis associated with inhibition of VEGF signalling. Furthermore, fistula formation and pneumonia have been reported in subjects treated with cabozantinib and should be considered as clinically indicated in subjects presenting with pulmonary symptoms.

## **20 ELECTROLYTE ABNORMALITIES**

Electrolyte abnormalities, including hypocalcaemia, hypokalaemia, hypomagnesaemia, and hypophosphataemia have been noted in subjects treated with cabozantinib. In some cases, these have been Grade 3 or 4 and/or serious. These laboratory values should be evaluated routinely. Deficits should be corrected when an electrolyte abnormality is noted in order to avoid worsening. Correction of electrolyte abnormalities should be accompanied by increased frequency of monitoring.

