#### **5.4      Laboratory Assessments**

The complete list of laboratory assessments to be performed in this study are indicated in [Section 8.2](#).

Based on an average treatment duration of 8 months and 12 visits, the total volume of blood drawn for all evaluations throughout this study will be approximately 144 mL for each subject (12 ml at each visit; this volume may depend on the laboratory used, treatment duration and number of visits).

All samples will be analysed locally.

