Warnings, precautions and guidelines for the management of AEs (e.g. GI disorders, hepatobiliary disorders, blood system disorders, constitutional disorders, skin disorders, hypertension, thromboembolic events, proteinuria, QTc prolongation, hypophosphataemia, thyroid function disorders, haemorrhagic events, GI perforation/fistula and non-GI fistula formation and osteonecrosis of the jaw (ONJ)) are provided in [Appendix 4](#).

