#### **6.2.4 Cabozantinib Warnings, Precautions and Guidelines for Management of Potential Adverse Events**

The side effect profile of cabozantinib includes, in descending order of frequency, diarrhoea, fatigue, decreased appetite, nausea, palmar-plantar erythrodysesthesia syndrome (PPES), vomiting, weight decreased, hypertension, constipation, dysphonia and asthenia (please refer to the Investigator's Brochure for additional details).

Subjects may also experience other medically important but less frequent AEs including arterial and venous thrombotic AEs (e.g. deep vein thrombosis (DVT), pulmonary embolism, TIA and MI), severe haemorrhagic events, proteinuria, wound healing complications, GI perforation, abscesses including intra-abdominal and pelvic abscess, GI and non-GI fistulae formation, osteonecrosis, and reversible posterior leukoencephalopathy syndrome (RPLS).

All AEs associated with laboratory abnormalities experienced by  $\geq 5\%$  of subjects treated with cabozantinib in descending order of frequency were anaemia, AST increased, ALT increased, hypothyroidism, hypokalaemia, hypomagnesaemia, thrombocytopenia, hypocalcaemia, hypophosphataemia, lactate dehydrogenase (LDH) increased, lipase increased, neutropenia, alkaline phosphatase (ALP) increased, hyponatraemia, and leukopenia.

All AEs should be managed with supportive care at the earliest signs of toxicity and dose reductions or study treatment interruptions should be considered. Dose reductions are recommended for events that, if persistent, could become serious or intolerable. A more detailed approach for management of potential AEs is provided in [Appendix 4](#).

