#### *8.1.2.4 Laboratory Test Abnormalities*

Abnormalities in laboratory test values should only be reported as AEs if any of the following apply:

- They result in a change in IMP schedule of administration (change in dosage, delay in administration, IMP discontinuation);
- They require intervention or a diagnosis evaluation to assess the risk to the subject;
- They are considered as clinically significant by the Investigator.

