#### **8.2 Clinical Laboratory Tests**

Blood and urine samples will be collected at the frequency indicated in [Table 2](#) for the evaluation of haematology, blood biochemistry, urinalysis, pregnancy tests and other clinical laboratory tests as safety measurements. A list of all laboratory analyses that will be measured in this study is provided in [Table 5](#).

All laboratory tests to establish eligibility must be done within 15 days prior to baseline ([Table 2](#)).

All laboratory analyses will be performed and analysed by the local laboratory, including samples that are obtained at unscheduled visits whenever possible. All local laboratory results will be recorded on the eCRF and provided by the Investigator. The Investigator will review the safety laboratory test results, document the review and record any clinically relevant changes occurring or observed during the study in the AE section of the eCRF (see [Section 8.1.2.4](#) for abnormal laboratory tests that should be recorded as AEs).

On days when a blood sample is collected, subjects must fast overnight (consumption of water is allowed).

Abnormalities in any clinical laboratory test (including tests not required per protocol) that lead to a change in subject management (e.g. dose withheld or reduced, study treatment discontinued; requirement for additional medication or monitoring) are considered clinically significant for the purposes of this study and should be reported as AEs. If laboratory values constitute part of an event that meets criteria defining it as serious, the event (and associated laboratory values) must be reported as an SAE (see [Section 8.1.4](#)).

All clinically relevant abnormal laboratory tests occurring during the study will be repeated at appropriate intervals until they return to baseline levels or to a level deemed acceptable by the Investigator or until the abnormality is explained by an appropriate diagnosis.

Table 5 Laboratory Assessments

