Haematology 
 
- White blood cells with differential count (absolute neutrophil count (ANC), basophils, eosinophils, lymphocytes and monocytes
 
- Haematocrit
 
- Platelet count
 
- Red blood cell count
 
- Haemoglobin
 
	Blood Chemistry 
 
- Albumin
 
- Total alkaline phosphatase (ALP)
 
- Alanine aminotransferase (ALT)
 
- Aspartate aminotransferase (AST)
 
- Blood urea nitrogen (BUN)
 
- Chloride
 
- Creatinine (estimation of creatinine clearance by Cockcroft and Gault)
 
- <math>\gamma</math>-glutamyl transpeptidase (GGT)
 
- Glucose
 
- Potassium
 
- Sodium
 
- Corrected calcium
 
- Total bilirubin (conjugated and unconjugated if total bilirubin is elevated)
 
- Total protein
 
	Pregnancy Blood/Urine Test 
 
- <math>\beta</math>-human chorionic gonadotrophin (<math>\beta</math>-HCG)
 
 Urinalysis (Dipstick or Routine)a 
 
- pH
 
- Protein
 
- Glucose
 
- Blood
 
 Microscopic Urine Examinationa 
 
- At the discretion of the Investigator based on results or routine urinalysis or as clinically indicated
 
 Urine Chemistry (at the discretion of the Investigator and based on results of routine urinalysis or as clinically indicated)a 
 
- 24-hour urine protein or urine protein-to-creatinine ratio (UPCR)
 

Coagulation 
 
- Prothrombin time/International normalised ratio (INR)
 
- Partial thromboplastin time (PTT)
 
		
Thyroid function 
 
- Thyroid-stimulating hormone (TSH)
 
- Free Thyroxine 4 (FT4)
 
		

a Fresh urine samples will be collected to perform these assessments.

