| 12-lead ECG | ≤15 Days prior to baseline | X (prior to first dose) ^f | | X | | Every 12 weeks | X | |
| Haematology and blood biochemistry | ≤15 Days prior to baseline | X (prior to first dose) ^f | X | X | X | Every 4 weeks | X | |
| Coagulation assessments | ≤15 Days prior to baseline | X (prior to first dose) ^f | X | X | X | Every 4 weeks | | |
| Urinalysis, microscopic urine examination and urine chemistry (including UPCR) ^g | ≤15 Days prior to baseline | X (prior to first dose) ^f | X | X | X | Every 4 weeks | X | |
| Pregnancy test (female subjects only, if applicable) | ≤7 days prior to baseline | X (prior to first dose) ^f | Urinary and/or pregnancy blood tests are mandatory at every visit | | | | X | |
| Thyroid function test (FT4, TSH) | ≤15 days prior to baseline | X (prior to first dose) ^f | Every 4 weeks | | | | X | |
| Chest/Abdomen/Pelvis (C/A/P) CT/MRI | ≤28 days prior to baseline | X ^f | Every 12 weeks (±10 days) while on protocol treatment beginning at Week 12 (i.e. Week 12, Week 24, Week 36, etc) until the end of study and additionally if clinically indicated | | | | | X ^h |
| Brain CT/MRI and Bone scintigraphy Scan (only if indicative of metastases) | ≤28 days prior to baseline | Only if indicative of brain and/or bone metastases at screening or if signs or symptoms suggestive of metastases develop | | | | | | X ^h (only if indicative of metastases) |

CONFIDENTIAL

SAP Final: Version 6.0: 17 August 2023

| | Pre-treatment Period | Treatment Period | | | | | | Post-treatment Follow-up Period ^d |
|--|-----------------------------------|---|---|------------------------|------------------------|---------------------------------|--|--|
| Assessment | Screening | Baseline ^a | Week 2 | Week 4 | Week 8 | Every 4 weeks | End of Study Treatment Visit ^b or Early Study Withdrawal Visit ^c | Follow-Up |
| | Visit 1 | Visit 2 | Visit 3 | Visit 4 | Visit 5 | Visit 6 to Visit X | 30 days after the last dose of treatment | Every 12 weeks |
| | Before first cabozantinib intake | Day 1 | Day 15 (± 2 Days) | Day 29 (± 2 Days) | Day 57 (± 2 Days) | Day 85 to Day X (± 5 Days) | (+15 Days) | (± 15 Days) |
| Cabozantinib intake ⁱ | | All subjects will be treated with oral cabozantinib 60 mg once daily (q.d.). In case of treatment-emergent toxicity, the Investigator may decide to reduce the dose to 40 mg or 20 mg | | | | | | |
| Dispense/return of oral study drug and compliance accounting | | X | | X | X | X | X | |

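### Magnesium and phosphate are to be evaluated routinely under Appendix 4, but neither is in the laboratory panel or the schedule

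*Protocol*

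**What the plan says.** Appendix 4, section 20, lists four electrolyte abnormalities seen with cabozantinib, notes that some were Grade 3 or 4 or serious, and states: "These laboratory values should be evaluated routinely". It gives no frequency, but asks for closer monitoring once a deficit is being corrected.

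Protocol section 6.2.4 lists, in descending frequency, the laboratory-related AEs seen in at least 5% of cabozantinib subjects. The middle of that list reads "hypokalaemia, hypomagnesaemia, thrombocytopenia, hypocalcaemia, hypophosphataemia, lactate dehydrogenase (LDH) increased, lipase increased, neutropenia". Section 6.2.2 refers investigators to Appendix 4 for managing a set of AEs that includes "QTc prolongation, hypophosphataemia, thyroid function disorders".

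On what is measured, protocol section 5.4 says "The complete list of laboratory assessments to be performed in this study are indicated in" section 8.2, and section 8.2 says "A list of all laboratory analyses that will be measured in this study is provided in" Table 5. The blood chemistry column of Table 5 includes potassium, sodium, chloride and "Corrected calcium". It includes neither magnesium nor phosphate. SAP Table 1 gives the same panel. The schedule in SAP section 1.3.3 has one row for "Haematology and blood biochemistry" and none for either analyte.

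**The concern.** The protocol tells investigators to check four electrolytes routinely, then defines a panel, presented as complete, that contains two of them. A site that follows the schedule exactly will never measure magnesium or phosphate unless something prompts it.

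Two things are at stake. The first is patient care: a deficit that produces no symptoms or ECG change may be found late, and the instruction to monitor more often after correction has no starting frequency to build on. The second is the safety data. The by-visit, CTCAE-grade and shift summaries in SAP section 3.2.2.2.1 have no planned source values for these analytes. Cases appear only as AEs, including in Table 14.3.1.12, beside abnormalities tested on schedule. A reader could compare those rates as if detection had been equal.

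**Working it through.** The check is mainly textual, with two short counts and one date calculation. The plan states no figure to reproduce.

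**1. The four named electrolytes against the panel and schedule**

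| Electrolyte | Protocol Table 5 | SAP Table 1 | Scheduled test |
|---|---|---|---|
| Calcium | Yes (corrected) | Yes (corrected) | Yes, with blood biochemistry |
| Potassium | Yes | Yes | Yes, with blood biochemistry |
| Magnesium | No | No | None |
| Phosphate | No | No | None |

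Result: 2 of 4 have no scheduled test. SAP section 1.3.2.2 sets blood biochemistry at Baseline, Weeks 2, 4 and 8, then every 4 weeks, but this reaches only the analytes in the panel. The two chemistry lists agree with each other. The amendment forms record removal of LDH, cholesterol and triglycerides from the panel, but no decision about magnesium or phosphate.

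**2. The laboratory AEs in protocol section 6.2.4**

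In order: anaemia, AST, ALT, hypothyroidism, hypokalaemia, hypomagnesaemia (6th), thrombocytopenia, hypocalcaemia, hypophosphataemia (9th), LDH, lipase, neutropenia, ALP, hyponatraemia, leukopenia. That is 15.

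- Without a scheduled test: magnesium, phosphate, LDH, lipase = 4. With one: 15 − 4 = 11.
- Scheduled and ranked below hypomagnesaemia: thrombocytopenia, hypocalcaemia, neutropenia, ALP, hyponatraemia, leukopenia = 6.
- Scheduled and ranked below hypophosphataemia: the last four of those = 4.

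So the panel does not simply stop at the more frequent effects: several less frequent ones are scheduled and these two are not.

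**3. Other routes to a test or a record**

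- Protocol section 5.3 lets the investigator add laboratory parameters. This is discretionary.
- Appendix 4, section 16, calls for an electrolyte check, magnesium in particular, once averaged ECGs confirm QTcF prolongation. This is triggered by an event, and phosphate is not named.
- Section 8.1.2.4 makes an abnormal value an AE if it changes dosing, needs intervention or evaluation, or meets the criterion "They are considered as clinically significant by the Investigator". Section 8.2 extends AE reporting to tests outside the protocol that change management. Both require that someone ordered the test.

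None of these sets a frequency.

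**4. How much could still be collected**

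Assume the last first dose was by 30 June 2022, the latest inclusion date in protocol section 3.6.

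- Final analysis cut-off: + 12 months = 30 June 2023, before SAP v6.0 (17 August 2023).
- End of study: + 18 months = 30 December 2023.
- 17 August to 30 December 2023 = 14 + 30 + 31 + 30 + 30 = 135 days; 135 / 7 = 19.3 weeks; 19.3 / 4 = 4.8.

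That leaves at most 4 to 5 four-weekly draws, and only in subjects still on treatment. SAP section 5 says the end of recruitment followed country-level amendment approvals, so the true dates could be later.

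**5. Which tables such draws could support**

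SAP section 3.2.2.2 defines laboratory baseline as the last value before first dose. Subjects first tested late in treatment have no such value, so grade-shift and change-in-toxicity tables cannot be built for them. Post-baseline values can only be listed or summarised. The follow-up output list (SAP Appendix 4) repeats Table 14.3.1.12 but contains no laboratory value table or listing.

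**The case against.** The best defence is that Appendix 4 is programme-wide guidance. It refers to individual protocols for dose levels and to a central ECG laboratory, whereas this trial reads ECGs locally. On that view, routine evaluation is advice on clinical care, and Table 5 separately defines the study dataset. Leaving two analytes out of that dataset is a tenable choice for an approved drug with a known laboratory profile in a phase II trial with an ORR endpoint. Section 20 also tells investigators to correct deficits they find. Correction is an intervention and so makes the finding an AE, which means detected deficits should mostly be reported.

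Much of this stands. It confines the gap largely to deficits nobody tested for, and the documents do not describe local testing practice. It does not remove the mismatch, because Appendix 4 is part of this protocol and sections 6.2.2 and 6.2.4 direct investigators to it. Rewording section 20 to testing as clinically indicated would cure the inconsistency but not the uneven ascertainment.

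A reader might go further and infer a specific shortfall, for example by applying an assumed detection share to the 5% threshold in section 6.2.4. The documents do not support that. The 5% is a floor on AE frequency in earlier cabozantinib experience, not a fully ascertained rate, and neither document gives a detection share.

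**Conclusion.** The mismatch is certain from the text: 2 of the 4 electrolytes that section 20 says to evaluate routinely are missing from the panel and the schedule. Both are listed effects of the drug. Testing is left to site discretion or, for magnesium, to a QTcF trigger, so late detection and under-ascertainment are possible and may differ between sites. The size of that effect cannot be estimated from the documents, and it depends on local practice that they do not describe.

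The same lack of comparability applies to LDH and lipase, which section 6.2.4 also lists and the panel also omits. The difference is that section 20 does not ask for them to be tested routinely.

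It would be wrong to infer that cases go unreported altogether: those found and acted on, needing evaluation, or judged significant enter the TEAE tables. The primary ORR analysis and the sample size are unaffected. This is a low-cost improvement to monitoring and safety reporting, not a flaw in the trial's main conclusion.

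**What to change.** **Panel.** Add magnesium and phosphate to the blood chemistry list in protocol Table 5 and SAP Table 1, on the existing biochemistry schedule and using blood already drawn. The cost is two local assays per visit, an eCRF and database update, and a protocol amendment, which under protocol section 13.1.1 generally needs prior ethics approval. With at most 4 to 5 draws left on the dates above, do this here only if enough subjects remain on treatment. A later protocol using the same panel can adopt it from the start.

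**Any values collected.** For subjects without a pre-dose value, list or summarise post-baseline results only, with no grade-shift tables. Add that output to SAP Appendix 4.

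**Subjects treated without scheduled tests.** Add a footnote to Table 14.3.1.12, at both the final and follow-up analyses, and one sentence in the report. Both should state that magnesium, phosphate, LDH and lipase were not systematically measured and that rates of the related abnormalities are not comparable with those of scheduled analytes. Name all four, since naming two would imply that the others were tested on schedule. The cost is one sentence and one footnote.

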**Appendix 5 Response Evaluation Criteria in Solid Tumours (RECIST) 1.1**

Adapted from (29).

## **TUMOUR MEASURABILITY**

At baseline, tumour lesions/lymph nodes will be categorized as measurable or non-measurable as described below. All measurable and non-measurable lesions should be assessed at screening and at subsequent protocol-specified tumour assessment timepoints. Additional assessments may be performed as clinically indicated for suspicion of progression.

## **DEFINITION OF MEASURABLE LESIONS**

### Tumour Lesions

Tumour lesions must be accurately measured in at least one dimension (longest diameter in the plane of measurement is to be recorded) with a minimum size as follows:

- 10 mm by computed tomography (CT) or magnetic resonance imaging (MRI) scan (CT/MRI scan slice thickness/interval  $\leq 5$  mm)
- 10-mm caliper measurement by clinical examination (lesions that cannot be accurately measured with calipers should be recorded as non-measurable)
- 20 mm by chest X-ray

### Malignant Lymph Nodes

To be considered pathologically enlarged and measurable, a lymph node must be  $\geq 15$  mm in the short axis when assessed by CT scan (CT scan slice thickness recommended to be  $\leq 5$  mm). At baseline and follow-up, only the short axis will be measured and followed. Additional information on lymph node measurement is provided below (see "Identification of Target and Non-Target Lesions" and "Calculation of Sum of Diameters").

## **DEFINITION OF NON-MEASURABLE LESIONS**

Non-measurable tumour lesions encompass small lesions (longest diameter  $< 10$  mm or pathological lymph nodes with short axis  $\geq 10$  mm but  $< 15$  mm) as well as truly non-measurable lesions. Lesions considered truly non-measurable include leptomeningeal disease, ascites, pleural or pericardial effusion, inflammatory breast disease, lymphangitic involvement of skin or lung, peritoneal spread, and abdominal mass/abdominal organomegaly identified by physical examination that is not measurable by reproducible imaging techniques.

## **SPECIAL CONSIDERATIONS REGARDING LESION MEASURABILITY**

Bone lesions, cystic lesions, and lesions previously treated with local therapy require particular comment, as outlined below.

Bone Lesions:

- Technetium-99m bone scans, sodium fluoride positron emission tomography scans, and plain films are not considered adequate imaging techniques for measuring bone lesions. However, these techniques can be used to confirm the presence or disappearance of bone lesions.
- Lytic bone lesions or mixed lytic-blastic lesions with identifiable soft tissue components that can be evaluated by cross-sectional imaging techniques such as CT or MRI can be

considered measurable lesions if the soft tissue component meets the definition of measurability described above.

- Blastic bone lesions are non-measurable.

#### Cystic Lesions:

- Lesions that meet the criteria for radiographically defined simple cysts should not be considered malignant lesions (neither measurable nor non-measurable) since they are, by definition, simple cysts.
- Cystic lesions thought to represent cystic metastases can be considered measurable lesions if they meet the definition of measurability described above.  
However, if non-cystic lesions are present in the same patient, these are preferred for selection as target lesions.

